Appendix C Handling of Human Biological Samples

C 1 Chain of Custody

A full chain of custody is maintained for all samples throughout their lifecycle.

The Investigator at each center keeps full traceability of collected biological samples from the participants while in storage at the center until shipment or disposal (where appropriate) and records relevant processing information related to the samples while at site.

The sample receiver keeps full traceability of the samples while in storage and during use until used or disposed of or until further shipment and keeps record of receipt of arrival and onward shipment or disposal.

AstraZeneca or delegated representatives will keep oversight of the entire life cycle through internal procedures, monitoring of study sites, auditing or process checks, and contractual requirements of external laboratory providers.

Samples retained for further use will be stored in the AstraZeneca-assigned biobanks or other sample archive facilities and will be tracked by the appropriate AstraZeneca Team during for the remainder of the sample life cycle.

If required, AstraZeneca will ensure that remaining biological samples are returned to the site according to local regulations or at the end of the retention period, whichever is the sooner.

C 2 Withdrawal of Informed Consent for Donated Biological Samples

AstraZeneca ensures that biological samples are returned to the source or destroyed at the end of a specified period as described in the informed consent.

If a participant withdraws consent to the use of donated biological samples, the samples will be disposed of/destroyed/repatriated, and the action documented. If samples are already analyzed, AstraZeneca is not obliged to destroy the results of this research.

Following withdrawal of consent for biological samples, further study participation should be considered in relation to the withdrawal processes outlined in the informed consent.

The Investigator:

- Ensures participant's withdrawal of informed consent to the use of donated samples is highlighted immediately to AstraZeneca or delegate.
- Ensures that relevant human biological samples from that participant, if stored at the study site, are immediately identified, disposed of as appropriate, and the action documented.

- Ensures that the participant and AstraZeneca are informed about the sample disposal.

AstraZeneca ensures the organization(s) holding the samples is/are informed about the withdrawn consent immediately and that samples are disposed of or repatriated as appropriate, the action is documented, and study site is notified.

C 3 International Airline Transportation Association 6.2 Guidance Document

LABELING AND SHIPMENT OF BIOHAZARD SAMPLES

International Airline Transportation Association (IATA) (<https://www.iata.org/whatwedo/cargo/dgr/Pages/download.aspx>) classifies infectious substances into 3 categories: Category A, Category B or Exempt.

Category A Infectious Substances are infectious substances in a form that, when exposure to it occurs, is capable of causing permanent disability, life-threatening or fatal disease in otherwise healthy humans or animals.

Category A Pathogens are, eg, Ebola, Lassa fever virus. Infectious substances meeting these criteria which cause disease in humans or both in humans and animals must be assigned to UN 2814. Infectious substances which cause disease only in animals must be assigned to UN 2900.

Category B Infectious Substances are infectious Substances that do not meet the criteria for inclusion in Category A. Category B pathogens are, eg, Hepatitis A, C, D, and E viruses. They are assigned the following UN number and proper shipping name:

- UN 3373 – Biological Substance, Category B
- are to be packed in accordance with UN 3373 and IATA 650

Exempt - Substances which do not contain infectious substances or substances which are unlikely to cause disease in humans or animals are not subject to these Regulations unless they meet the criteria for inclusion in another class.

- Clinical study samples will fall into Category B or exempt under IATA regulations
- Clinical study samples will routinely be packed and transported at ambient temperature in IATA 650 compliant packaging (<https://www.iata.org/whatwedo/cargo/dgr/Documents/DGR-60-EN-PI650.pdf>)
- Biological samples transported in dry ice require additional dangerous goods specification for the dry-ice content

Appendix D Actions Required in Cases of Increases in Liver Biochemistry and Evaluation of Hy's Law

D 1 Introduction

This Appendix describes the process to be followed in order to identify and appropriately report Potential Hy's Law (PHL) cases and Hy's Law (HL) cases. It is not intended to be a comprehensive guide to the management of elevated liver biochemistries.

During the course of the study the Investigator will remain vigilant for increases in liver biochemistry. The Investigator is responsible for determining whether a participant meets potential PHL criteria at any point during the study.

All sources of laboratory data are appropriate for the determination of PHL and HL events; this includes samples taken at scheduled study visits and other visits including central and all local laboratory evaluations even if collected outside of the study visits; for example, PHL criteria could be met by an elevated ALT from a central laboratory **and/or** elevated TBL from a local laboratory.

The Investigator will also review Adverse Event data (for example, for AEs that may indicate elevations in liver biochemistry) for possible PHL events.

The Investigator participates, together with AstraZeneca clinical project representatives, in review and assessment of cases meeting PHL criteria to agree whether HL criteria are met. HL criteria are met if there is no alternative explanation for the elevations in liver biochemistry other than Drug Induced Liver Injury (DILI) caused by the IMP.

The Investigator is responsible for recording data pertaining to PHL/HL cases and for reporting SAEs and AEs according to the outcome of the review and assessment in line with standard safety reporting processes.

D 2 Definitions

Potential Hy's Law

Aspartate aminotransferase (AST) or Alanine Aminotransferase (ALT) $\geq 3 \times$ Upper Limit of Normal (ULN) **together with** Total Bilirubin (TBL) $\geq 2 \times$ ULN at any point during the study following the start of study medication irrespective of an increase in Alkaline Phosphatase (ALP).

Hy's Law

AST or ALT $\geq 3 \times$ ULN **together with** TBL $\geq 2 \times$ ULN, where no other reason, other than the IMP, can be found to explain the combination of increases, eg, elevated ALP indicating cholestasis, viral hepatitis, another drug.

For PHL and HL the elevation in transaminases must precede or be coincident with (ie, on the same day) the elevation in TBL, but there is no specified timeframe within which the elevations in transaminases and TBL must occur.

D 3 Identification of Potential Hy's Law Cases

In order to identify cases of PHL it is important to perform a comprehensive review of laboratory data for any participant who meets any of the following identification criteria in isolation or in combination:

- ALT $\geq 3 \times$ ULN
- AST $\geq 3 \times$ ULN
- TBL $\geq 2 \times$ ULN

Central Laboratories Being Used:

When a participant meets any of the PHL identification criteria, in isolation or in combination, the central laboratory will immediately send an alert to the Investigator (also sent to AstraZeneca representative).

The Investigator will also remain vigilant for any local laboratory reports where the PHL identification criteria are met, where this is the case the Investigator will:

- Notify the AstraZeneca representative
- Request a repeat of the test (new blood draw) by the central laboratory without delay
- Complete the appropriate unscheduled laboratory eCRF module(s) with the original local laboratory test result

When the identification criteria are met from central or local laboratory results the Investigator will without delay:

- Determine whether the participant meets PHL criteria (see Appendix D 2 for definition) by reviewing laboratory reports from all previous visits (including both central and local laboratory results)

Local Laboratories Being Used:

The Investigator will without delay review each new laboratory report and if the identification criteria are met will:

- Notify the AstraZeneca representative

- Determine whether the participant meets PHL criteria (see Appendix [D 2](#) for definition) by reviewing laboratory reports from all previous visits
- Promptly enter the laboratory data into the laboratory eCRF

D 4 Follow-up

D 4.1 Potential Hy's Law Criteria not met

If the participant does not meet PHL criteria the Investigator will:

- Inform the AstraZeneca representative that the participant has not met PHL criteria.
- Perform follow-up on subsequent laboratory results according to the guidance provided in the CSP.

D 4.2 Potential Hy's Law Criteria met

If the participant does meet PHL criteria the Investigator will:

- Notify the AstraZeneca representative who will then inform the central Study Team
- Within 1 day of PHL criteria being met, the Investigator will report the case as an SAE of Potential Hy's Law; serious criteria "Important medical event" and causality assessment "yes/related" according to CSP process for SAE reporting
- For participants that met PHL criteria prior to starting IMP, the Investigator is not required to submit a PHL SAE unless there is a significant change¹ in the participant's condition
- The Study Physician contacts the Investigator, to provide guidance, discuss and agree an approach for the study participants' follow-up (including any further laboratory testing) and the continuous review of data
- Subsequent to this contact the Investigator will:
 - Monitor the participant until liver biochemistry parameters and appropriate clinical symptoms and signs return to normal or baseline levels, or as long as medically indicated. Completes follow-up SAE Form as required.

¹ A 'significant' change in the participant's condition refers to a clinically relevant change in any of the individual liver biochemistry parameters (ALT, AST or TBL) in isolation or in combination, or a clinically relevant change in associated symptoms. The determination of whether there has been a significant change will be at the discretion of the investigator, this may be in consultation with the Study Physician if there is any uncertainty.

- Investigate the etiology of the event and perform diagnostic investigations as discussed with the Study Physician. This includes deciding which the tests available in the Hy's Law lab kit should be used.
- Complete the 3 Liver eCRF Modules as information becomes available.

D 5 Review and Assessment of Potential Hy's Law Cases

The instructions in this section should be followed for all cases where PHL criteria are met.

As soon as possible after the biochemistry abnormality was initially detected, the Study Physician contacts the Investigator in order to review available data and agree on whether there is an alternative explanation for meeting PHL criteria other than DILI caused by the IMP, to ensure timely analysis and reporting to health authorities within 15 calendar days from date PHL criteria was met. The AstraZeneca Global Clinical Head or equivalent and Global Safety Physician will also be involved in this review together with other subject matter experts as appropriate.

According to the outcome of the review and assessment, the Investigator will follow the instructions below.

Where there is an agreed alternative explanation for the ALT or AST and TBL elevations, a determination of whether the alternative explanation is an AE will be made and subsequently whether the AE meets the criteria for a SAE:

- If the alternative explanation is **not** an AE, record the alternative explanation on the appropriate eCRF
- If the alternative explanation is an AE/SAE: update the previously submitted Potential Hy's Law SAE and AE eCRFs accordingly with the new information (reassessing event term; causality and seriousness criteria) following the AstraZeneca standard processes.

If it is agreed that there is **no** explanation that would explain the ALT or AST and TBL elevations other than the IMP:

- Send updated SAE (report term “Hy's Law”) according to AstraZeneca standard processes.
 - The “Medically Important” serious criterion should be used if no other serious criteria apply
 - As there is no alternative explanation for the HL case, a causality assessment of “related” should be assigned.

If, there is an unavoidable delay, of over 15 calendar days in obtaining the information necessary to assess whether or not the case meets the criteria for HL, then it is assumed that there is no alternative explanation until such time as an informed decision can be made:

- Provides any further update to the previously submitted SAE of Potential Hy's Law, (report term now "Hy's Law case") ensuring causality assessment is related to IMP and seriousness criteria is medically important, according to CSP process for SAE reporting.
- Continue follow-up and review according to agreed plan. Once the necessary supplementary information is obtained, repeat the review and assessment to determine whether HL criteria are still met. Update the previously submitted PHL SAE report following CSP process for SAE reporting, according to the outcome of the review and amending the reported term if an alternative explanation for the liver biochemistry elevations is determined.

D 6 Laboratory Tests

The list below represents the standard, comprehensive list of follow-up tests which are recommended but not mandatory when using a central laboratory. For studies using a local laboratory, the list may be modified based on clinical judgment. Any test results need to be recorded.

Hy's Law Lab Kit for Central Laboratories

Additional standard chemistry and coagulation tests	GGT LDH Prothrombin time INR
Viral hepatitis	IgM anti-HAV HBsAg IgM and IgG anti-HBc HBV DNA ^a IgG anti-HCV HCV RNA ^b IgM anti-HEV HEV RNA
Other viral infections	IgM & IgG anti-CMV IgM & IgG anti-HSV IgM & IgG anti-EBV
Alcoholic hepatitis	Carbohydrate deficient transferrin (CD-transferrin) ^c
Autoimmune hepatitis	Antinuclear antibody (ANA) Anti-Liver/Kidney Microsomal Ab (Anti-LKM) Anti-Smooth Muscle Ab (ASMA)

Metabolic diseases	alpha-1-antitrypsin Ceruloplasmin Iron Ferritin Transferrin ^c Transferrin saturation
--------------------	--

^a HBV DNA is only recommended when IgG anti-HBc is positive

^b HCV RNA is only recommended when IgG anti-HCV is positive or inconclusive

^c CD-transferrin and Transferrin are not available in China. Study teams should amend this list accordingly

D 7 References

Aithal et al, 2011

Aithal et al 2011, Clinical Pharmacology and Therapeutics 89(6):806-815.

FDA Guidance for Industry, July 2009

FDA Guidance for Industry (issued July 2009) 'Drug-induced liver injury: Premarketing clinical evaluation'. Available from; <https://www.fda.gov/regulatory-information/search-fda-guidance-documents/drug-induced-liver-injury-premarketing-clinical-evaluation>

Appendix E Hospitalization Definition

Amid a rising number of COVID-19 hospitalizations across the world, leading to a shortage of hospital beds, temporary facilities are being utilized increasingly to manage severe COVID-19 patients who would have usually been treated in a traditional hospital setting.

Please note that in this protocol, “hospitalization” is defined as ≥ 24 hours of acute care, in a hospital or similar acute care facility, including emergency rooms or temporary facilities instituted to address medical needs of those with severe COVID-19 during the COVID-19 pandemic.

For the purposes of ascertaining an exclusion criterion or an endpoint event, individuals with COVID-19 will be considered “hospitalized” if they are:

- 1 Managed in an alternative care site set up or authorized by states, provinces, or equivalent jurisdictions or
- 2 Provided with acute hospital care at home meeting the criteria below:
 - (a) Physician determines the patient’s condition as being appropriate for “acute inpatient hospitalization”
 - (b) Treating physician should have appropriate screening protocols before care at home begins, to assess both medical and non-medical factors, including patient’s preference, working utilities and assessment of physical barriers
 - (c) Patients are evaluated daily either in person or remotely by a qualified health care provider/treating physician and are managed appropriately based on the patient’s treatment plan and local standards for COVID-19 management.

The appropriate WHO Clinical Progression Scale for COVID-19 score assigned to grade the participant’s condition would depend on the level of oxygen/ventilation support provided in these acute care settings.

Appendix F Anaphylaxis

Anaphylaxis is highly likely when either of the following criteria are fulfilled:

- 1 Acute onset of an illness (minutes to several hours) with involvement of the skin, mucosal tissue, or both (eg, generalized hives, pruritus or flushing, swollen lips, tongue and/or uvula) plus features of anaphylaxis involving one or more system ([Table 18](#)) OR
- 2 Hypotension, bronchospasm, or upper airway obstruction

Table 18 Clinical Features of Anaphylaxis in Children

System	Features of anaphylaxis
Respiratory (most common in children)	Persistent cough Wheeze, stridor, hoarse voice, difficulty talking or change in character of cry Tongue swelling Chest pain or dyspnoea Subjective feeling of swelling, tightness or tingling the throat or mouth
Cardiovascular	Pale and floppy (infant) Palpitations, tachycardia, bradycardia Hypotension, pallor Collapse with or without unconsciousness Cardiac arrest
Neurological	Headache (usually throbbing) Dizziness Altered consciousness, confusion, sudden behavior change
Gastrointestinal	Nausea, vomiting, dysphagia Diarrhoea Abdominal or pelvic pain
Dermatological	Urticarial rash Erythema, flushing, tearing Angioedema Pruritus (skin, eyes, nose, throat, mouth)

Source: [RCH 2021](#).

The following definitions are provided for the purposes of this study:

Hypersensitivity reaction: An acute onset of an illness with involvement of the skin, mucosal tissue, or both after injection of IMP (but does not meet the definition of anaphylaxis described above).

To assist with the mitigation of these AEs, see [Table 19](#), which categorizes reactions by severity of symptoms and proposes severity-specific treatment and offers guidance on management of IMP. Final treatment is at the discretion of the Investigator and should reflect local standard of care.

Table 19 An Approach to Management of Anaphylactic, Hypersensitivity, and Post Injection/Infusion Reactions

Severity of symptoms	Treatment	Investigational product

Mild local reactions (During and post injection/infusion and hypersensitivity)
 
Mild injection/infusion site reactions such as redness, mild swelling, pain at the injection site or headache, nausea, non-pruritic rash, or mild hypersensitivity reactions including localized at the injection site or generalized cutaneous reactions such as mild pruritus, flushing, rash, dizziness, headache, ≤ 20 mmHg change in systolic BP from pre-administration measurement.
	
Evaluate participant, including close monitoring of vital signs.
 
At the discretion of the Investigator, treat participant, for example, with:
 
Localized cold pack or heat to the injection site. If more generalized reaction:
 
 • Diphenhydramine or equivalent and/or • Acetaminophen or equivalent dose of paracetamol and/or • Topical antihistamines and/or low-potency topical corticosteroid preparations and/or • Anti-nausea medication, as needed. 
Doses and route of administration as per local standard of care.
	
Pause or hold additional IMP injection immediately.
 
At the discretion of the Investigator, resume current IMP administration under observation.

Moderate reactions (during or immediately post injection)
 
Injection/infusion site reaction such as those listed above under mild reactions but excluding moderate hypersensitivity reactions (see below).
	
Evaluate participant, including close monitoring of vital signs.
 
Treat participant, for example, with:
 
 • Normal saline IV and/or • Diphenhydramine 50 mg IV or equivalent and/or • Acetaminophen 500 to 650 mg or equivalent dose of paracetamol and/or • Anti-nausea and/or antiemetic intramuscular, as needed. 
Doses and route of administration as per local standard of care.
	
Stop or hold additional IMP administration immediately.
 
At the discretion of the Investigator, resume current IMP administration under observation.

Moderate hypersensitivity reactions
 
Reactions which may include generalized rash or urticaria, palpitations, chest discomfort, shortness of breath, hypo- or hypertension with
	
Evaluate participant, including close monitoring of vital signs.
 
Treat participant, for example, with:
 
 • Normal saline IV and/or 	
Stop IMP administration immediately.

Table 19 An Approach to Management of Anaphylactic, Hypersensitivity, and Post Injection/Infusion Reactions

Severity of symptoms	Treatment	Investigational product
> 20 mmHg change in systolic BP from pre-infusion measurement.	
 Diphenhydramine or equivalent and/or Acetaminophen or equivalent dose of paracetamol and/or IV corticosteroids, such as hydrocortisone or methylprednisolone. 
Doses and route of administration as per local standard of care.
	

Severe Above plus fever with rigors, hypo- or hypertension with ≥ 40 mmHg change in systolic BP, signs of end-organ dysfunction (eg, symptomatic hypotension such as hypotonia, syncope, incontinence, seizure) from pre-infusion measurement, or wheezing, angioedema, or stridor
 
OR
 
Life-threatening Defined as a reaction that is life-threatening and requires pressor and/or ventilator support or shock associated with acidemia and impairing vital organ function due to tissue hypoperfusion
	
Evaluate participant, including close monitoring of vital signs. Maintain airway, oxygen if available. Treat participant immediately, for example with:
 
 Normal saline IV Epinephrine for bronchospasm, hypotension unresponsive to IV fluids, or angioedema IV corticosteroids, such as hydrocortisone or methylprednisolone Diphenhydramine or equivalent Acetaminophen or equivalent dose of paracetamol 
Doses and route of administration as per local standard of care. Call emergency medical transport for transport to emergency hospital based on judgment of the Investigator. Grade 3 wheezing, hypotension or angioedema is unresponsive to single dose of epinephrine Grade 4 event At the discretion of the Investigator
	
Stop IMP administration immediately. Do not resume current dosing. Permanently discontinue IMP administration. Consider need for additional oral antihistamine administration or oral corticosteroid administration to prevent reoccurrence of symptoms over subsequent 2 to 3 days.

BP, blood pressure; IMP, investigational medicinal product; IV, intravenous;

RCH 2021

The Royal Children's Hospital (RCH) Melbourne. Clinical Practice Guidelines. Anaphylaxis.
Available from: https://www.rch.org.au/clinicalguide/guideline_index/Anaphylaxis/ Accessed
22 September 2021.

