5.1 Inclusion Criteria

Participants are eligible to be included in the study only if all the following criteria apply:

Age and Weight

- 1 Participant must be aged \geq 29 weeks GA to $<$ 18 years of age at the time of signing the informed consent (see Appendix A 3 for procedures around informed consent).
- 2 Participant must weigh a minimum of 1.5 kg.

Type of Participant and Disease Characteristics

COHORT 1: Participants who do not have COVID-19 and have not knowingly been exposed to a SARS-CoV-2 positive individual (pre-exposure prophylaxis):

- 3 At increased risk of severe COVID-19 for any of the following reasons:
 - (a) Immunocompromised state
 - (b) One or more comorbid conditions that increase the risk of severe COVID-19, eg, cardiovascular disease, including heart disease since birth, malignancy, chronic kidney disease, and genetic, neurologic, or metabolic conditions.
- 4 Medically stable defined as disease not requiring significant change in therapy or hospitalization for worsening disease during the one month prior to enrollment, with no acute change in condition at the time of study enrollment as judged by the Investigator.
- 5 Documented negative SARS-CoV-2 RT-PCR test collected \leq 3 days prior to Day 1 or a negative rapid SARS-CoV-2 antigen test at screening.
- 6 Prior to enrollment, participants must not have had COVID-19 symptoms (Table 13) within 10 days of dosing.

7 Increased risk for SARS-CoV-2 infection, defined as those whose locations or circumstances put them at appreciable risk of exposure to SARS-CoV-2 and COVID-19, based on available risk assessment at time of enrollment.

COHORT 2: Participants with COVID-19 and mild to moderate symptoms (treatment):

8 At increased risk of severe COVID-19 for any of the following reasons:

- (a) Immunocompromised state
- (b) One or more comorbid conditions that increase the risk of severe COVID-19 (see list in 3[b])

9 Medically stable defined as disease not requiring significant change in therapy or hospitalization for worsening disease during the one month prior to enrollment, with no acute change in condition at the time of study enrollment as judged by the Investigator.

10 Documented positive SARS-CoV-2 RT-PCR test collected \leq 3 days prior to Day 1 or a positive rapid SARS-CoV-2 antigen test at screening.

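### Minor, wrong as written: Appendix F lets a skin-only reaction meet the anaphylaxis definition, because criterion 1 does not exclude the Dermatological row of Table 18

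*Protocol*

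**What the plan says.** **The definition.** Protocol Appendix F gives two alternative criteria. The first is an acute illness involving skin or mucosa, with hives, itching and flushing among its examples, "plus features of anaphylaxis involving one or more system", followed by a reference to Table 18. The second is low blood pressure, bronchospasm or upper-airway obstruction.

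**Table 18** lists five systems: respiratory, cardiovascular, neurological, gastrointestinal and dermatological. The dermatological row reads "Urticarial rash Erythema, flushing, tearing Angioedema Pruritus", with body sites added after the last item.

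**Hypersensitivity** is defined next, as an acute skin or mucosal illness after dosing, with the limit "but does not meet the definition of anaphylaxis described above".

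**Table 19** sets out management by severity, with the lead-in "Final treatment is at the discretion of the Investigator and should reflect local standard of care". Its mild row places widespread itching, flushing and rash under mild hypersensitivity. Its moderate hypersensitivity row covers "Reactions which may include generalized rash or urticaria, palpitations, chest discomfort, shortness of breath, hypo- or hypertension with" a systolic change above 20 mmHg. Its moderate reactions row prints "Diphenhydramine 50 mg IV or equivalent and/or" and "Acetaminophen 500 to 650 mg or equivalent dose of paracetamol and/or". Section 5.1 sets the lower weight limit: "Participant must weigh a minimum of 1.5 kg".

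**Where the definition is used.** Protocol 8.3.4.1 sends the reader to Appendix F for the definition. Protocol 8.3.4 lists as AESIs anaphylaxis and, beyond it, only serious hypersensitivity reactions. Protocol 7.4.2 cites Appendix F in a stopping criterion met by one related anaphylactic reaction. SAP 4.2.2.1 lists Anaphylaxis, Hypersensitivity and Serious Hypersensitivity Reaction as separate AESI entries categorized in the eCRF, and SAP Table 2 names anaphylaxis within the primary safety endpoint.

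**The concern.** A definition that separates anaphylaxis from a skin reaction should require something beyond the skin. Criterion 1 seems meant to do so, but its second half accepts any Table 18 system, including the one that repeats the skin signs of the first half. Taken at its word, it classes ordinary urticaria as anaphylaxis.

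Three things depend on the definition: the AESI category, whether a non-serious skin reaction is an AESI at all under the protocol's list, and the one-event stopping criterion. In the first pediatric study of this product, a single case wrongly reported as anaphylaxis would be noticed by anyone reading the safety results.

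A separate wording problem lies in the same appendix. One row of Table 19 gives fixed drug amounts in a protocol whose participants range from newborns to adolescents.

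**Working it through.** The plan states no figure here, so the check is a logical one.

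**Step 1. The rule.** Criterion 1 = (acute skin or mucosal involvement) AND (at least one feature in at least one Table 18 system). Neither the sentence nor a table footnote says *other* or *non-skin*.

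**Step 2. Test case.** Generalized hives and itching, with no respiratory, cardiovascular, neurological or gastrointestinal sign.

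| Part of the rule | Result as written | Result if the second half excludes the skin |
|---|---|---|
| Skin or mucosal involvement | met | met |
| Feature in a Table 18 system | met (Dermatological) | not met |
| Criterion 2 | not met | not met |
| Class | anaphylaxis | hypersensitivity reaction |

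The examples in the first half (hives, itching, flushing) also appear in the Dermatological row, so for these cases the second half adds no requirement.

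**Step 3. Effect on the hypersensitivity class.** That class is whatever skin or mucosal illness fails the anaphylaxis definition. As written, only skin signs missing from Table 18 are left in it. The mild row of Table 19, which treats widespread itching, flushing and rash as mild hypersensitivity, fits the right-hand column and conflicts with the left.

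**Step 4. Effect on AESI counts, per relabelled event.**
- SAP 4.2.2.1 list: +1 Anaphylaxis, −1 Hypersensitivity; total change 0.
- Protocol 8.3.4 list, non-serious event that is not an injection or infusion site reaction: 0 AESIs if classed as hypersensitivity, 1 if classed as anaphylaxis; total change +1.

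SAP 4.2.2.1 summarizes AESI incidence by cohort and route and specifies no split by AESI category. The relabelling would show in the individual AE listing, which identifies AESIs. The table shells are not among the documents.

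**Step 5. Fixed doses in the moderate reactions row.**
- Diphenhydramine: 50 / 1.5 = 33.3 mg/kg at the minimum weight; 50 / 40 = 1.25 mg/kg at 40 kg.
- Acetaminophen: 500 / 1.5 = 333 and 650 / 1.5 = 433 mg/kg at the minimum weight; 500 / 40 = 12.5 and 650 / 40 = 16.25 mg/kg at 40 kg.

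The other three rows of Table 19 name these drugs without an amount.

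**The case against.** The best defence is that the intended meaning is plain. A reading that makes the second half redundant and nearly empties the next definition is unlikely to be what the authors meant, and Table 19 supports the sensible reading. The lead-in to the criteria speaks of likelihood, investigators categorize AESIs in the eCRF, and the stopping criterion also requires relatedness. The error is over-inclusive, so it errs towards caution.

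Most of this stands, and it is why the point is minor. It does not remove the point: the hypersensitivity definition and Section 8.3.4.1 both treat this text as the definition, and no other text corrects the wording.

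A reader might infer three stronger things that the documents do not support.

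- *That Table 19 contains a second classification error.* Urticaria with palpitations, from the moderate hypersensitivity row, would still meet criterion 1 after the correction, and hypotension meets criterion 2. But Table 19 guides management by severity and does not assign categories. A clarifying sentence is useful, not essential.
- *That the fixed doses direct an overdose in small infants.* The cell presents its drugs as examples, allows equivalents and leaves dose and route to local practice. The figures in Step 5 show why fixed amounts do not belong there, not what anyone would be told to give.
- *That adult data limit the number of affected events.* Protocol 2.3.1 reports no hypersensitivity reactions among 60 dosed adults, and the exact 95% upper limit is 1 − 0.025^(1/60) = 5.96%. Multiplying by 46 gives 2.7, but that is an expected count at the limit, not a maximum: at 5.96% the chance of more than 3 events in 46 is about 29%. Those adults were also healthy volunteers in a study that SAP Table 5 describes as placebo-controlled. No range should be given.

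**Conclusion.** Minor, and wrong as written. Criterion 1 classes a skin-only reaction as anaphylaxis, probably through a missing word. Under the SAP's list the AESI total is unchanged and one event moves between categories; under protocol 8.3.4 a non-serious skin-only reaction would wrongly be added as an AESI. The number of such events is unknown and may be zero.

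It should not be inferred that any event was misclassified or that recruitment was held wrongly. The documents report no such event, and investigators may have applied the intended meaning. SAP Section 2 states that enrolment has stopped, with 46 participants in the full analysis set, and protocol 6.1.1 gives each participant one dose on Day 1, so the stopping and acute-treatment consequences are past. What remains is the correct category for any such event in the report. This assumes that the Appendix F wording governs classification, as Section 8.3.4.1 says, and that the database is still open.

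**What to change.** - **(a) Definition.** Reword the second half of criterion 1 to *one or more other (non-dermatological) systems (Table 18)*. Optionally add that the Appendix F definition, and not the Table 19 severity row, decides the AESI category and the 7.4.2 criterion.
- **(b) Case check.** Before lock, compare every event reported as Anaphylaxis or Hypersensitivity with the corrected definition, document the result, and keep the reported eCRF category visible in the AE listing.
- **(c) Doses.** As a separate safety-wording correction, delete the diphenhydramine and acetaminophen amounts from the moderate reactions row. The cell's deferral to local practice already covers dosing.

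Items (a) and (c) are wording changes in one appendix and put the text right. Item (b) is the only one that can still affect this study's report. It needs no new data or procedures and covers only the cases reported, possibly none.
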